12. MEASUREMENT OF EFFECT

12.1 Antitumor Effect – Solid Tumors

For the purposes of this study, participants should be re-evaluated for response every 8 weeks during the first six months of the study, then every 12 weeks, in both arms. Response and progression will be evaluated in this study using the international criteria proposed by the Response Evaluation Criteria in Solid Tumors (RECIST) guideline (version 1.1). Changes in the largest diameter (unidimensional measurement) of the tumor lesions and the shortest diameter in the case of malignant lymph nodes are used in the RECIST criteria.

12.1.1 Definitions

Evaluable for Target Disease response. Only those participants who have measurable disease present at baseline, have received at least one cycle of therapy, and have had their disease re-evaluated will be considered evaluable for target disease response. These participants will have their response classified according to the definitions stated below. (Note: Participants who exhibit objective disease progression prior to the end of cycle 1 will also be considered evaluable.)

Evaluable Non-Target Disease Response. Participants who have lesions present at baseline that are evaluable but do not meet the definitions of measurable disease, have received at least one cycle of therapy, and have had their disease re-evaluated will be considered evaluable for non-target disease. The response assessment is based on the presence, absence, or unequivocal progression of the lesions.

12.1.2 Disease Parameters

Measurable disease. Measurable lesions are defined as those that can be accurately measured in at least one dimension (longest diameter to be recorded) as ≥ 10 mm with CT scan, MRI, or calipers by clinical exam. All tumor measurements must be recorded in millimeters (or decimal fractions of centimeters).

Note: Tumor lesions that are situated in a previously irradiated area might not be considered measurable.

Malignant lymph nodes. To be considered pathologically enlarged and measurable, a lymph node

must be ≥ 15 mm in short axis when assessed by CT scan (CT scan slice thickness recommended to be no greater than 5 mm). At baseline and in follow-up, only the short axis will be measured and followed.

Non-measurable disease. All other lesions (or sites of disease), including small lesions (longest diameter <10 mm or pathological lymph nodes with ≥ 10 to <15 mm short axis), are considered non-measurable disease. Bone lesions, leptomeningeal disease, ascites, pleural/pericardial effusions, lymphangitis cutis/pulmonitis, inflammatory breast disease, abdominal masses (not followed by CT or MRI), and cystic lesions are all considered non-measurable.

Note: Cystic lesions that meet the criteria for radiographically defined simple cysts should not be considered as malignant lesions (neither measurable nor non-measurable) since they are, by definition, simple cysts.

‘Cystic lesions’ thought to represent cystic metastases can be considered as measurable lesions, if they meet the definition of measurability described above. However, if non-cystic lesions are present in the same participant, these are preferred for selection as target lesions.

Target lesions. All measurable lesions up to a maximum of 2 lesions per organ and 5 lesions in total, representative of all involved organs, should be identified as **target lesions** and recorded and measured at baseline. Target lesions should be selected on the basis of their size (lesions with the longest diameter), be representative of all involved organs, but in addition should be those that lend themselves to reproducible repeated measurements. It may be the case that, on occasion, the largest lesion does not lend itself to reproducible measurement in which circumstance the next largest lesion which can be measured reproducibly should be selected. A sum of the diameters (longest for non-nodal lesions, short axis for nodal lesions) for all target lesions will be calculated and reported as the baseline sum diameters. If lymph nodes are to be included in the sum, then only the short axis is added into the sum. The baseline sum diameters will be used as reference to further characterize any objective tumor regression in the measurable dimension of the disease.

Non-target lesions. All other lesions (or sites of disease) including any measurable lesions over and above the 5 target lesions should be identified as **non-target lesions** and should also be recorded at baseline. Measurements of these lesions are not required, but the presence, absence, or in rare cases unequivocal progression of each should be noted throughout follow up. If a target lesion is biopsied at screening, this lesion must be followed as non-target lesions after the biopsy unless it is the patients only target lesion. If there is only one target lesion, it should be followed as a target lesion regardless.

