3. PARTICIPANT SELECTION

3.1 Eligibility Criteria

- 3.1.1 Histologically or cytologically confirmed unresectable advanced or metastatic renal cell carcinoma with clear cell component. Patient with extensive sarcomatoid histology are accepted.
- 3.1.2 Participants must have failed or developed an intolerance to at least 1 prior anti-VEGFR systemic therapy and 1 immune checkpoint inhibitor for metastatic RCC. No limit on the number of prior lines of therapies.
- 3.1.3 Measurable disease as per RECIST 1.1. See section 12 for the evaluation of measurable disease.
- 3.1.4 Age ≥ 18 years
- 3.1.5 ECOG performance status ≤ 2 (Karnofsky $\geq 60\%$, see **Appendix A**)
- 3.1.6 Participants must undergo fresh tumor biopsy unless medically unsafe or not feasible.
- 3.1.7 Normal organ and marrow function as defined below:
 - Absolute neutrophil count $\geq 1,500/\text{mcL}$
 - Platelets $\geq 100,000/\text{mcL}$
 - Hemoglobin $\geq 10\text{g/dL}$ (transfusions allowed)
 - Total bilirubin $\leq 2.0 \times$ institutional upper limit of normal with the following exception: patients with known Gilbert disease should have a serum bilirubin $\leq 3 \times \text{ULN}$
 - AST(SGOT)/ALT(SGPT) $\leq 3.0 \times$ institutional upper limit of normal with the following exception: patients with known liver metastases should have AST and ALT $\leq 5 \times \text{ULN}$
 - Creatinine clearance $\geq 30 \text{ mL/min}/1.73 \text{ m}^2$ according to the Cockcroft-Gault equation. (APPENDIX F)
 - Urine protein/creatinine ratio (UPC ratio) ≤ 2

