3.2 Exclusion Criteria

A patient will be excluded from the study if he or she meets any of the following criteria:

- 3.2.1 Patients receiving any other investigational agents.
- 3.2.2 Patients who received prior CDK4/6 inhibitors.
- 3.2.3 For Arm 2 only, patients who have received prior HIF-2 α inhibitor.
- 3.2.4 Participants who have received any continuous or intermittent small molecule therapeutics (excluding monoclonal antibodies) \leq 4 effective half-lives prior to starting study drug or who have not recovered from side effects of such therapy to grade 1 or less (except for non-clinically significant laboratory abnormalities).
- 3.2.5 Patients must have discontinued all biologic therapy including therapeutic antibodies at least 28 days before C1D1.
- 3.2.6 Participants who have received wide field radiotherapy \leq 4 weeks or limited field radiation for palliation \leq 2 weeks prior to starting study drug or who have not recovered from side effects of such therapy to at least grade 1.
- 3.2.7 Participants with untreated metastatic ccRCC to the brain may participate in this trial if clinically and radiographically stable per investigator's assessment and not on corticosteroid (equivalent to $>/=$ 10 mg prednisone) or antiepileptic therapy.

- 3.2.8 O2 saturation <92% by arterial blood gas analysis or pulse oximetry on room air
- 3.2.9 Untreated deep vein thrombosis or pulmonary embolism, or event of deep vein thrombosis or pulmonary embolism within 2 weeks of treatment start. Patient should be on at least 1 week of anticoagulation before C1D1.
- 3.2.10 The patient has serious and/or uncontrolled preexisting medical condition(s) that, in the judgment of the investigator, would preclude participation in this study (for example, interstitial lung disease, severe dyspnea at rest or requiring oxygen therapy, severe renal impairment [e.g. estimated creatinine clearance <30ml/min], history of major surgical resection involving the stomach or small bowel, or preexisting Crohn's disease or ulcerative colitis or a preexisting chronic condition resulting in baseline Grade 2 or higher diarrhea)."

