5.5.3 Restricted therapy

Local anticancer therapies can be considered in case of progression or clinical indication. Those include radiation therapy, thermal ablation, surgery. Limited data are available with abemaciclib and radiotherapy. Thus, caution should be exercised with coadministering abemaciclib with radiotherapy. Sponsor must be contacted in these situations to ensure adequate risks related to the procedure and concomitant study treatment. In this situation where a target lesion is treated by such procedure, the participant may continue the study but may not be evaluable for response. However, the patient might remain evaluable for progression after discussion with the study sponsor.

Abemaciclib is predominantly cleared by oxidative metabolism via CYP3A4. Clinical drug interaction studies with a CYP3A inhibitor and CYP3A inducer significantly altered the PK of abemaciclib and its circulating major metabolites.

CYP3A inducers:

Avoid concomitant use of CYP3A inducers (**Appendix B**) and consider alternative agents.

CYP3A inhibitors:

Avoid concomitant use of strong CYP3A inhibitors (for example, voriconazole) and use caution with coadministered moderate (for example, ciprofloxacin) or weak (for example, ranitidine) CYP3A inhibitors. If coadministration with a strong CYP3A inhibitor is unavoidable, reduce the abemaciclib dose by one dose level (**Table 5**) or, in the case of ketoconazole, reduce the abemaciclib dose by two dose levels. In patients who have had a dose reduction by one dose level due to adverse reactions, further reduce the abemaciclib dose to dose level -2 (**Table 5**). Avoid grapefruit or grapefruit juice. If a CYP3A inhibitor is discontinued, increase the abemaciclib dose (after 3-5 half-lives of the inhibitor) to the dose that was used before starting the inhibitor.

In vitro studies in primary cultures of human hepatocytes indicate that abemaciclib might inhibit the metabolism of CYP2B6 substrate drugs in vivo. Based on this finding, sensitive substrates of CYP2B6 such as bupropion and efavirenz should be substituted or avoided if possible.

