1: Baseline evaluations are to be conducted within 28 days prior to the start of therapy, at the exception of the serum pregnancy test that must be performed within 7 days of therapy start. Scans must be done within 28 days prior to the start of therapy. All baseline screening should be done prior to registration.

2: A cycle will be defined as 28 days.

3: Imaging assessments, quality of life assessments will take place:

- every 8 weeks (+/- 7 days) for the first 6 months.

- After 6 months, imaging assessments and quality of life assessments can take place every 12 weeks (+/- 10 days)

4: Patients who discontinue from treatment will be asked to return to the clinic no more than 30 days after the last treatment for a treatment discontinuation visit. The visit at which a response assessment shows progressive disease may be used as the treatment discontinuation visit.

5: After progression/treatment discontinuation, participants will be followed for survival and receipt of next line therapies every 6 months until death or 2 years after treatment discontinuation. Participants removed from protocol therapy with ongoing treatment-related adverse event(s) will be followed until resolution or stabilization of the adverse event(s), initiation of new cancer-directed treatment, or death. Participants removed from protocol who did not experience disease progression will be followed as per protocol until progression, initiation of new cancer-directed treatment, or death.

6: Physical examination should include general description of participant, head, eyes, ears, nose, and throat, chest, abdominal, extremities, neurologic, skin, and lymph node examination. Any other evaluation is up to the discretion of the practitioner. It will not be considered a violation if the exam is not described as outlined here.

7: Vital signs include blood pressure, heart rate, respiratory rate, body temperature and pulse oximetry.

8: Hematology testing to include full CBC with WBC, ANC, hemoglobin, and platelet count and differential.

9: Serum chemistry to include full comprehensive metabolic panel with sodium, potassium, chloride, bicarbonate, BUN, creatinine, glucose, calcium, albumin, magnesium, and LDH.

10: Liver function tests to include AST, ALT, total bilirubin, and direct bilirubin

11: Coagulation factors to include PT, aPTT, and INR.

12: Pregnancy test only needs to be obtained in women of childbearing potential, within 7 days of therapy start.

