12.1.3 Methods for Evaluation of Disease

All measurements should be taken and recorded in metric notation using a ruler, calipers, or a digital measurement tool. All baseline evaluations should be performed as closely as possible to the beginning of treatment and never more than 4 weeks before the beginning of the treatment.

The same method of assessment and the same technique should be used to characterize each identified and reported lesion at baseline and during follow-up. Imaging-based evaluation is preferred to evaluation by clinical examination unless the lesion(s) being followed cannot be

imaged but are assessable by clinical exam.

Clinical lesions. Clinical lesions will only be considered measurable when they are superficial (*e.g.*, skin nodules and palpable lymph nodes) and ≥ 10 mm in diameter as assessed using calipers (*e.g.*, skin nodules). In the case of skin lesions, documentation by color photography, including a ruler to estimate the size of the lesion, is recommended.

Conventional CT and MRI. This guideline has defined measurability of lesions on CT scan based on the assumption that CT thickness is 5mm or less. If CT scans have slice thickness greater than 5 mm, the minimum size of a measurable lesion should be twice the slice thickness. MRI is also acceptable in certain situations (*e.g.* for body scans).

Use of MRI remains a complex issue. MRI has excellent contrast, spatial, and temporal resolution; however, there are many image acquisition variables involved in MRI, which greatly impact image quality, lesion conspicuity, and measurement. Furthermore, the availability of MRI is variable globally. As with CT, if an MRI is performed, the technical specifications of the scanning sequences used should be optimized for the evaluation of the type and site of disease. Furthermore, as with CT, the modality used at follow-up should be the same as was used at baseline and the lesions should be measured/assessed on the same pulse sequence. It is beyond the scope of the RECIST guidelines to prescribe specific MRI pulse sequence parameters for all scanners, body parts, and diseases. Ideally, the same type of scanner should be used and the image acquisition protocol should be followed as closely as possible to prior scans. Body scans should be performed with breath-hold scanning techniques, if possible.

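### Lesions irradiated shortly before entry can be used as target lesions, so radiation shrinkage can count toward the primary ORR, mainly in patients with one or two targets

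*Combined protocol and SAP*

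**What the plan says.** Four sets of rules bear on this.

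- **Measurability.** Section 12.1.2 notes: "Tumor lesions that are situated in a previously irradiated area might not be considered measurable". It does not say when such a lesion is or is not measurable. Section 3.1.3 does not add a test of its own: "Measurable disease as per RECIST 1.1. See section 12 for the evaluation of measurable disease".
- **Target selection.** Section 12.1.2: "Target lesions should be selected on the basis of their size (lesions with the longest diameter), be representative of all involved organs". Reproducibility of measurement is the remaining criterion. Prior radiation is not mentioned. The same section does handle one other screening intervention: a target lesion biopsied at screening is moved to non-target unless it is the only one.
- **Timing.** Section 3.2.6 sets two washouts, 4 weeks for wide-field radiotherapy and 2 weeks for "limited field radiation for palliation". Footnote 1 of the study calendar in section 11 says: "Scans must be done within 28 days prior to the start of therapy". Section 12.1.3 asks for baseline evaluations as near to treatment as possible and "never more than 4 weeks before the beginning of the treatment". Nothing ties the scan to the end of radiotherapy.
- **Local therapy.** Section 5.5.3, on therapy restricted during the study: "In this situation where a target lesion is treated by such procedure, the participant may continue the study but may not be evaluable for response".

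A PR is a fall of at least 30% from the baseline sum (section 12.1.4.1). PR or CR as best response, by central review, is the ORR endpoint in both arms (section 14.1.1).

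**The concern.** The 2-week washout is shorter than the 28-day scan window. A lesion can be measured, then irradiated, then followed on study drug with the pre-radiation size as its baseline. Even when the scan follows the radiation, a lesion treated a little over two weeks before first dose may still be shrinking from it. Because the measurability note is permissive and unconditional, one site or reader may accept such a lesion and another reject it, and both comply with the plan.

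The plan already accepts the principle in section 5.5.3: local treatment of a target lesion can spoil the response assessment. Radiation between the baseline scan and day 1 affects the sum in the same way, but no clear rule covers it.

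The stake is attribution. Neither arm has a control group, so any shrinkage caused by radiation is credited to the study drug, and the error runs in one direction, toward a higher ORR. With 20 patients and a cut-off of 7, a single such case can matter.

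**Working it through.** **1. Is the path open?** Count days before first dose.

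- Limited-field radiation is barred at 14 days or fewer, so it is permitted from day -15 backwards.
- The oldest permitted scan is at day -28.
- Radiation after that scan can therefore fall from day -27 to day -15, which is 27 - 15 + 1 = 13 days.
- Wide-field radiation is barred at 28 days or fewer, equal to the scan window, so it cannot fall between scan and first dose.

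**2. Who is exposed?** Section 12.1.2 classes bone lesions as non-measurable, so irradiated bone cannot be a target. That leaves soft-tissue, visceral and nodal lesions. With m equal-sized targets and the others unchanged, one irradiated lesion must shrink by 0.30 × m to produce a PR alone:

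| Targets (m) | Shrinkage needed in the irradiated lesion |
|---|---|
| 1 | 30% |
| 2 | 60% |
| 3 | 90% |
| 4 or 5 | not possible (over 100%) |

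Unequal sizes change these figures: a lesion holding share w of the baseline sum must shrink by 0.30/w. The exposure is mainly in patients with one or two targets, or with one dominant target.

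**3. The plan's own design figures (section 14.2).** Exact binomial tail: P(X ≥ r | n, p) = Σ C(n,x) pˣ (1-p)ⁿ⁻ˣ, summed from x = r to n.

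- Arm 2, n = 20, r = 7: 0.0867 at p = 0.20 (stated one-sided alpha 0.09) and 0.942 at p = 0.50 (stated power 94%).
- Arm 1, n = 11, r = 2: 0.803 at p = 0.25 (stated 0.80).

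All three reproduce.

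**4. Sensitivity of the Arm 2 rule at a true ORR of 20%.** The documents give no frequency of pre-entry radiation, so both devices below are assumptions. Either a share q of true non-responders is scored as responders because of radiation, giving p = 0.20 + 0.80q. Or one patient is a certain false responder, and 6 or more responses are needed from the other 19.

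| Assumption | Calculation | Chance of ≥ 7 of 20 |
|---|---|---|
| No false responses | P(X ≥ 7 given 20, 0.200) | 0.087 |
| q = 1% | P(X ≥ 7 given 20, 0.208) | 0.103 |
| q = 2.5% | P(X ≥ 7 given 20, 0.220) | 0.130 |
| One certain false responder | P(X ≥ 6 given 19, 0.200) | 0.163 |

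The expected number of false responders among 20 patients is 20 × 0.80 × q: 0.16 at q = 1% and 0.40 at q = 2.5%. The last row is conditional on a case having occurred.

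**The case against.** The strongest replies, and what stands of each:

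- **Section 12.1.3 asks for scans as near to treatment as possible.** Keeping a day -28 scan after irradiating a measured lesion goes against that. This stands as a limit on how often it would happen. It is guidance, though, and the only fixed limit is 4 weeks.
- **Section 5.5.3 may already cover it.** A lesion becomes a target when identified at baseline, so radiation after the scan arguably fits those words, and section 14.3.2 then counts a non-evaluable patient as a non-responder. The reading is possible. But that section speaks of a participant continuing on study and says only that response may not be evaluable. Under section 12.1.1 such a patient is evaluable.
- **Central review and confirmation.** A reader might infer that central review cannot correct the problem. The documents do not show that. The measurability note lets a reader reject such a lesion, and external sites are typically asked for prior-treatment records at registration (section 4.3). What is missing is a rule: footnote 16 of the calendar sends images and imaging reports, with no mention of radiation fields. Confirmation at 4 weeks or more does not separate lasting radiation shrinkage from drug effect.
- **Wide-field radiation.** A reader might infer that it is free of the problem. Only the scan-timing gap is specific to limited-field treatment; residual shrinkage after a longer washout is possible too.
- **Size.** Assuming a certain false responder assumes the harm, so the range has to start at zero effect. Two certain cases would give 0.284, but nothing in the documents supports expecting that many.
- **Arm 1.** A reader might treat 2 or more responses in 11 as a success rule and compute an inflated error rate from a low true ORR. Section 14.2 uses that count only to describe what would probably be seen at an ORR of 25% or higher. It states no decision rule and no null rate.

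**Conclusion.** The gap is real and bounded. A site and a central reader who both follow the plan can accept a recently irradiated soft-tissue, visceral or nodal lesion as a target, and can do so on a scan taken before the radiation. Any resulting response enters the primary ORR as drug effect. The bias can only be upward.

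Its size cannot be fixed from the documents. Under the stated assumptions, the Arm 2 chance of declaring the combination effective at a true ORR of 20% runs from 0.087 (no false responses) through 0.103 and 0.130 to 0.163 (one certain false responder). These figures take patients as independent. No error rate is claimed for Arm 1, although its ORR estimate is open to the same bias. The point justifies a change of wording, not a change of design.

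**What to change.** 1. In section 12.1.2, replace the permissive note with a condition: a lesion in a previously irradiated or otherwise locally treated area may be measurable or a target only if imaging after that treatment documented progression of that lesion; otherwise it is followed as non-target. Section 3.1.3 already refers to section 12, so eligibility follows.
2. State that a lesion irradiated between the baseline scan and day 1 cannot be a target on the strength of the pre-radiation scan, and cross-refer to this in footnote 1 of the study calendar.
3. In section 12.1.5, require that central readers receive the pre-study radiation fields and apply the same rule.

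The cost is wording, plus a few patients whose only measurable lesion was recently irradiated and who would not qualify, and some later or repeat baseline scans. Sample sizes, the cut-off of 7 in 20 and the radiotherapy washout stay as they are.
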